10.6 Subject Discontinuation or Withdrawal

- A. Subjects may be involuntarily removed from the study for failure to adhere to the protocol, failure to attend follow-up visits, or due to safety reasons. In such cases, the Investigator shall arrange for an exit visit and complete a study exit case report form for the subject.
- B. Subjects may voluntarily withdraw from the study at any time without reason. The Investigator shall make an effort to obtain an exit visit but cannot insist on the visit if the subject does not wish to come in. The Investigator shall complete a study exit case report form with as much information as is available at the time of withdrawal.
- C. In cases of early termination, as many of the month 12 study procedures should be performed as possible at the time of withdrawal. All information relative to the withdrawal must be fully documented in the subject chart.
- D. If the subject requires removal from the study due to medical reasons (i.e. adverse event) or reasons related to the procedure, the site staff should contact the Gynesonics Medical Director. Adverse device effects that are ongoing at the time of withdrawal will be reported and followed up to 6 weeks following the study treatment or until the adverse device effect resolves or is considered stable, whichever comes last, unless the subject has withdrawn consent for any such follow-up. In such cases, the final follow-up can be either a telephone contact or an office visit.
- E. A subject will be withdrawn from the study if, subsequent to enrollment, she is diagnosed with any condition that could affect menstrual bleeding volume, or if she becomes pregnant at any time following Sonata treatment. In the case of pregnancy, the Investigator and study coordinator should make every attempt to obtain basic pregnancy outcome information and complete the applicable case report form.
- F. A subject may be withdrawn after enrollment and before receiving the study treatment if, at the Investigator's discretion, she has developed a general health condition that would increase risks from study treatment

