5.6.1 Analysis Populations

The FAS population will be comprised of all study subjects who were treated and who do not meet any of the following criteria:

- Become pregnant during the 12-month post-procedure study period;
- Are diagnosed with a medical condition that would make assessment of menstrual bleeding invalid or unreliable.

The safety population will be comprised of subjects who were treated and have post-baseline information.

The per-protocol (PP) population will include subjects who complete 12 months of follow-up without study protocol violations. The PP population will include subjects from the FAS population who do not meet any of the following criteria:

- Violated the inclusion/exclusion criteria;
- Did not complete a 12 month PBAC;
- Are associated with protocol violations that are considered to influence the endpoint under evaluation;

Subjects who discontinue the study due to a device/procedure-related adverse event (AE) or documented lack of efficacy (without surgical reintervention) will be included in the PP population, with missing data imputed as failure for the 12-month menstrual blood loss (MBL) endpoint.

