5.6.4.2 Secondary Efficacy Analysis

There are six secondary endpoints:

- Change in total fibroid volume from Baseline to 12 months
- Change in perfused fibroid volume from Baseline to 12 months
- Change in UFS-QOL from Baseline to 12 months
- OTE at 12 months
- Subject satisfaction at 12 months
- Change in EQ-5D from Baseline to 12 months

Secondary endpoints will be summarized using descriptive statistics.

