5.6.8.2 Handling of Dropouts or Missing Data

Reduction in MBL at 12 Months

Missing 12-month menstrual blood loss data will be imputed using last observation carried forward (LOCF). Subjects which undergo surgical reintervention to manage fibroid symptoms prior to 12 months will be excluded from the Reduction in Menstrual Blood Loss analysis.

Surgical Reintervention for HMB due to Treatment Failure at 12 Months

Life-Table methods will be used to calculate the success rate and 95% confidence interval for the rate of surgical reintervention during 12 months. Therefore, subjects that are discontinued prior to 12 months for reasons other than surgical reintervention will be considered censored.

Sensitivity Analyses

Sensitivity analyses will also be conducted to examine the impact of missing data. A worst-case analysis (all missing data imputed as failures) and best-case analysis (all missing data imputed as successes) will be performed. In addition, a tipping point analysis will be performed.

Secondary Endpoint Analyses

No imputations will be made for missing secondary endpoint data.

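### The SAP has no rule for secondary outcomes after surgical reintervention, so by default post-surgery scores are summarised as device outcomes

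*SAP*

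**What the plan says.** - **Secondary endpoints.** SAP 5.6.4.2 lists six, among them "Change in UFS-QOL from Baseline to 12 months", EQ-5D, OTE, satisfaction and fibroid volume. The method is one sentence: "Secondary endpoints will be summarized using descriptive statistics". SAP 5.6 makes the FAS analysis primary and the per-protocol (PP) analysis supportive.
- **Missing data.** For secondary endpoints, SAP 5.6.8.2 states "No imputations will be made for missing secondary endpoint data".
- **Reintervention, MBL endpoint.** The same section states "Subjects which undergo surgical reintervention to manage fibroid symptoms prior to 12 months will be excluded from the Reduction in Menstrual Blood Loss analysis". There is no parallel sentence for the secondary endpoints.
- **Reintervention, life-table endpoint.** Reintervention is the event, and "subjects that are discontinued prior to 12 months for reasons other than surgical reintervention will be considered censored".
- **FAS.** SAP 5.6.1: "The FAS population will be comprised of all study subjects who were treated and who do not meet any of the following criteria". The two criteria are pregnancy and a diagnosed condition that undermines the bleeding assessment. Reintervention is not one of them.
- **Follow-up after reintervention.** At each visit where the question is asked (Protocol 12.3.B), the site records the procedure and its date. Nothing releases the woman from later assessments. Under the same visits, a pregnancy does release her.
- **Schedule.** Protocol Table 4 has UFS-QOL, EQ-5D, OTE and satisfaction at 12, 24 and 36 months, and MRI at 12 months.

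**The concern.** The authors saw that bleeding measured after surgery says nothing about the device, and they wrote a rule for MBL. The same reasoning applies to symptom and quality-of-life scores, but no rule was written for them. A woman whose device treatment failed and who then had a hysterectomy, myomectomy, embolization, focused ultrasound or endometrial ablation (the list in SAP 5.5.1.2) may have much better UFS-QOL and EQ-5D scores at 12 months. With no rule, a programmer who follows the SAP takes every observed 12-month value in the FAS, hers included.

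This is a single-arm study in which each woman is her own control, so no comparator arm carries the same distortion. At stake is whether the reported symptom and quality-of-life change describes the device, or the device plus the surgery done after it failed. The question returns at 24 and 36 months.

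**Working it through.** **1. Which women are affected.** Reintervention is not an FAS exclusion. Nor does it trigger withdrawal under Protocol 10.6, which names pregnancy and a new diagnosis: "A subject will be withdrawn from the study if, subsequent to enrollment, she is diagnosed with any condition that could affect menstrual bleeding volume". A hysterectomy is a procedure, not such a diagnosis. If reintervened women were already outside the FAS, the separate MBL exclusion would hardly be needed. They therefore remain in the primary analysis set for the secondary endpoints.

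**2. The plan's own figures.** Inputs are from Protocol 19.1 and SAP Table 4. The check uses an exact binomial with a lower limit at one-sided 0.025; for reintervention this stands in for the life-table limit.
- MBL: n = 125, threshold 45%, true rate 60%. At least 68 successes are needed; one-sided error 0.0218, power 0.914.
- Freedom from reintervention: n = 75, threshold 75%, true rate 90%. At least 64 successes are needed; one-sided error 0.0221, power 0.931.
- Protocol dropout: 125/0.85 = 147.06, against a stated 147.

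Both sample sizes reproduce, so no stated figure is in dispute.

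**3. How many women.** The plan assumes success of at least 90%, so q, the share reintervened, is at most 10% under its own assumption: 0.10 × 125 = 12.5 and 0.10 × 147 = 14.7. The most that can still pass the co-primary criterion is 21/125 (16.8%) or 26/147 (17.7%, exact lower limit 0.752).

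**4. Effect on a mean score.** Let D be the mean change in women without reintervention and S the mean change in reintervened women, measured after surgery.
- As observed: (1 − q)D + qS
- Reintervened women absent: D
- Reintervened women set to no change: (1 − q)D

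As observed minus absent is q(S − D) = q × d. As observed minus no change is qS. Absent minus no change is qD.

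The documents give no expected secondary values. I assume D = 20-30 and S = 40-60 points for a UFS-QOL type score, so d runs from 40 − 30 = 10 to 60 − 20 = 40. For EQ-5D the formulas hold on its own scale.

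| q | q × d | qS | qD |
|---|---|---|---|
| 2% | 0.2-0.8 | 0.8-1.2 | 0.4-0.6 |
| 10% | 1-4 | 4-6 | 2-3 |
| 17% | 1.7-6.8 | 6.8-10.2 | 3.4-5.1 |

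At 26/147 with d = 40, q × d = 0.177 × 40 ≈ 7.1 points.

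**5. Effect on a responder percentage.** Let s be the responder rate in the other women, assumed 60-80%. If every reintervened woman responds, the as-observed rate is (1 − q)s + q. Counted as failures it is (1 − q)s, so the gap is q: 10 percentage points at q = 10%. If these women are simply absent, the rate is s and the gap to failure is qs: 0.10 × 60 to 0.10 × 80, or 6-8 points.

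**The case against.** **The plan never says that post-surgery values are used.** Correct. A reader might take the no-imputation sentence as an instruction to use them, but it concerns missing values only. That the values enter as observed is inferred from FAS membership, continued visits and the lack of a rule.

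**Some wording suggests that reintervention ends follow-up.** The censoring sentence in SAP 5.6.8.2 speaks of women discontinued for reasons other than reintervention, and SAP 5.6.1 speaks of discontinuation for lack of efficacy without reintervention. Neither is a withdrawal rule, but both leave that reading open. The 12-month values would then be missing, and the distortion would come from losing known failures (the qD column). Protocol 10.6 also asks for as many month-12 procedures as possible at early termination, so post-surgery values could still arise. Both readings need a rule.

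**The direction is not the same for every endpoint.** A reader might infer that every route favours the device; the documents do not support that. Satisfaction is asked about the study treatment, and a woman who then needed a hysterectomy may rate it poorly. The screening UFS-QOL looks back over three cycles. If that recall also applies at follow-up, surgery shortly before month 12 may leave pre-surgery symptoms in the score. After hysterectomy a fibroid volume might be recorded as missing or as zero, and the plan does not say which. Ordinary dropout has no known direction.

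**The PP tables give some protection.** The SAP plans PP versions of the secondary tables, and the PP set excludes women for whom this applies: "Did not complete a 12 month PBAC". That removes most women with an earlier hysterectomy. A woman can still complete the chart after myomectomy or endometrial ablation, and PP is only supportive. The planned sensitivity table covers the co-primary endpoints only.

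**Consequences are limited.** The secondary endpoints carry no test or success criterion, and reintervention is reported as a co-primary. This stands.

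**Conclusion.** The gap is real. The SAP deals with reintervention for MBL and leaves it undefined for the secondary endpoints, and the default sends post-surgery values into the primary summary. The case is strongest for UFS-QOL and EQ-5D, weaker for OTE and satisfaction, and unresolved for fibroid volume.

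At 10% reintervention a mean score shifts by 1-4 points, and at about 17-18% by about 1.7-7 points. Responder percentages are up to 10 points higher at 10% than with reintervened women counted as failures. These sizes rest on the assumed D, S and s. They also assume that all reintervened women supply post-surgery values and, for the 10-point figure, that all of them respond. At 2% reintervention the mean shift is below 1 point.

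Two stronger readings fail. One is that the 75% goal tolerates 25% reintervention, giving 0.25 × 40 = 10 points. The criterion applies to the lower confidence limit: 37/147 reinterventions (110 successes) give an exact lower limit of 0.670, so that trial has already failed. The other is that study success is at risk; it is not, because both success criteria are co-primary. This should be corrected before analysis, but it does not undermine the trial's main conclusion.

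**What to change.** In SAP 5.6.4.2 and 5.6.8.2, state that values collected after surgical reintervention are not credited to the device, and say which procedures trigger the rule. The list in SAP 5.5.1.2 is available. The MBL exclusion refers to fibroid symptoms and the co-primary to HMB due to treatment failure, so the trigger should be explicit. Then, by endpoint:

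- **OTE and satisfaction:** count reintervened women as non-responders.
- **UFS-QOL and EQ-5D:** present a summary with post-reintervention values set to no change from baseline, beside the as-observed summary.
- **Fibroid volume:** state that MRI values after reintervention are not used as device shrinkage. Assigning the baseline volume is debatable here, because it would erase any real shrinkage before surgery.
- **All secondary tables:** report the number of women reintervened, and apply the same rule at 24 and 36 months.

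The SAP should also say whether reintervention ends follow-up, so that its discontinuation wording and the Protocol's visit instructions agree.

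The cost is a few sentences, extra summary columns and slightly smaller mean improvements. No new data are needed, since the procedure and its date are already recorded.

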5.6.4 Efficacy Analyses

Efficacy evaluations will be summarized descriptively, by visit.

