5.6.7 Determination of Sample Size

SAS® PROC POWER was used to calculate the following sample sizes. The co-primary endpoint of Reduction in MBL at 12 months will be analyzed using 95% exact confidence intervals. In order to claim study success, the lower limit of the 95% confidence interval must exceed the pre-specified threshold (described in the table below).

Table 4: Determination of Sample Size

Co-Primary Endpoint	Lower Confidence Limit Success Criterion	Assumed Subject Success Rate	N to Achieve 90% Power
Reduction in MBL at 12 months	≥45%	60%	125
Rate of surgical reintervention for HMB due to treatment failure at 12 months	≥75%	90%	75

To account for an assumed 20% subject dropout rate (subjects lost to follow-up), a sample size of at least 125 and up to 150 treated subjects will be enrolled.

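### The 12-month UFS-QOL, EQ-5D, OTE and satisfaction results are labelled FAS but are observed-case, with no missing-data sensitivity analysis, and may favour the device

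*SAP*

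**What the plan says.** SAP 5.6.4.2 fixes these endpoints at 12 months, for example "Change in UFS-QOL from Baseline to 12 months", "OTE at 12 months" and "Subject satisfaction at 12 months". The method is one sentence: "Secondary endpoints will be summarized using descriptive statistics". SAP 5.6.8.2 adds: "No imputations will be made for missing secondary endpoint data". SAP 5.6 makes the FAS primary. SAP 5.6.1 defines it as treated women, less those who become pregnant within 12 months or whose bleeding can no longer be assessed reliably. Tables 14.2.2.1 and 14.2.3.3.1 carry the FAS label for the secondary endpoints.

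Earlier data exist. SAP 5.6.4 says "Efficacy evaluations will be summarized descriptively, by visit". SAP Table 2 collects UFS-QOL and EQ-5D at 3, 6 and 12 months, and OTE and satisfaction from 6 months.

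Loss is expected. Protocol 19.1 assumes 15%. SAP 5.6.7 says "To account for an assumed 20% subject dropout rate (subjects lost to follow-up". SAP 5.6.1 also foresees women leaving because of a device- or procedure-related event or for lack of efficacy: those with "documented lack of efficacy (without surgical reintervention) will be included in the PP population, with missing data imputed as failure". That sentence goes on to limit the failure rule to 12-month menstrual blood loss (MBL).

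**The concern.** With no imputation and no model linking the visits, a woman without a 12-month value drops out of the 12-month mean or percentage. The table says FAS, but the number describes women observed at 12 months. If some women leave because the treatment did not help or harmed them, those who remain are a favourable selection. A single-arm trial has no comparator against which that selection could be judged.

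The co-primary endpoints are better protected. Missing MBL data are carried forward, reintervention is handled by life-table methods, and worst-case, best-case and tipping-point analyses follow. The four subject-reported outcomes have no equivalent. At stake is whether the reported 12-month improvement in symptoms, quality of life and satisfaction describes treated women or only those still under observation.

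**Working it through.** **1. The plan's own loss figures.** Protocol 19.1: 125 / (1 − 0.15) = 147.06, which reproduces the stated 147. Expected without 12-month data: 0.15 × 147 = 22 women. SAP 5.6.7: 20% loss with up to 150 treated gives 0.20 × 150 = 30 women missing and 120 observed. (150 equals 125 × 1.2; dividing gives 125 / 0.80 = 156.25. That is a separate matter. Only the loss fraction is used below.)

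**2. Who enters the 12-month figure.** No imputation (SAP 5.6.8.2) plus descriptive statistics at 12 months (SAP 5.6.4.2) means only women with a score counted as 12-month. Scores at 3 and 6 months enter their own by-visit rows and do not inform the 12-month row.

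**3. Is a sensitivity analysis planned?** The sensitivity paragraph of SAP 5.6.8.2 names no endpoint, but its worst and best cases are expressed as failures and successes. SAP 5.6.4.2 defines no success or failure for these outcomes, and the only sensitivity table in the index (14.2.3.2.3) is for the co-primaries.

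**4. Size for a mean change.** Let d be the share of FAS women without a 12-month score and f the leavers' mean change as a fraction of the observed mean. Then:

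all-FAS mean = observed mean × [(1 − d) + d·f]

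overstatement = 1 / [(1 − d) + d·f] − 1

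The documents supply d (0.15 or 0.20) but not f, so f is an assumption.

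| Assumed f | d = 0.15 | d = 0.20 |
|---|---|---|
| 1 (leavers like stayers) | 0% | 0% |
| 0.75 | 1/0.9625 − 1 = 3.9% | 1/0.95 − 1 = 5.3% |
| 0.5 | 1/0.925 − 1 = 8.1% | 1/0.90 − 1 = 11.1% |
| 0 (no improvement) | 1/0.85 − 1 = 17.6% | 1/0.80 − 1 = 25.0% |

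The middle rows have a second reading. If a share s of leavers had no improvement and the rest resembled stayers, then f = 1 − s. So f = 0.75 is one leaver in four without benefit, and f = 0.5 is one in two.

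**5. Size for a percentage.** All-FAS rate = (1 − d) × observed rate + d × leavers' rate. Assume, for illustration, 90% satisfied among women observed:

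| Assumed leavers' rate | d = 0.15 | d = 0.20 |
|---|---|---|
| 90% | 90% | 90% |
| 40% | 0.765 + 0.060 = 82.5% | 0.72 + 0.08 = 80.0% |
| 0% | 76.5% | 72.0% |

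**The case against.** The strongest defence is that the choice is stated openly and little depends on it. These endpoints have no hypothesis, threshold or test, and study success rests only on the two co-primaries. SAP 5.6 reports n with every continuous summary, so attrition will be visible. All of that stands and keeps the priority low. But n shows how many women are missing, not how they were doing.

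Four stronger readings are tempting, and the documents do not support them.

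- **That leavers' earlier scores are discarded.** They appear in the by-visit summaries (SAP 5.6.4, Table 14.2.2.1) and are absent only from the 12-month figure. OTE and satisfaction have no 3-month score to lose.
- **That the result is strictly completers-only.** Protocol 10.6, item C, asks for as much of the month-12 assessment as possible at early withdrawal. Women who formally exit may therefore have such scores. The SAP does not say whether they count as 12-month data, so the accurate description is observed-case with an undefined rule for exit scores.
- **That all 15–20% of losses are driven by poor outcome.** Both figures are allowances for loss to follow-up in general, and no number is given for exits for lack of efficacy. Pregnancies and diagnoses that invalidate bleeding assessment leave the FAS altogether, so they are not missing FAS data.
- **That the SAP already treats such women as failures and merely forgot to here.** The rule in 5.6.1 covers MBL in the per-protocol population only. In the FAS, missing MBL is carried forward.

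**Conclusion.** The point holds in a limited form. The 12-month UFS-QOL, EQ-5D, OTE and satisfaction results are observed-case under an FAS label, and no sensitivity analysis for missing data is planned for them. Because some exits for lack of efficacy or treatment-related events are foreseen, any bias may favour the device. That direction is an inference and not a demonstrated result.

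The size depends on how leavers fared, which the documents do not say. It runs from zero if they resemble stayers, through 8% or 11% at half the improvement, to 18% or 25% at no improvement, for 15% and 20% loss respectively. The upper figures require every missing woman to have gained nothing, and they are a bound under that assumption rather than an estimate. Study success does not change. This is a low-cost improvement to the description of benefit and does not undermine the trial's conclusion.

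**What to change.** Amend SAP 5.6.8.2 and 5.6.4.2, keeping the observed-case summary.

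1. For the UFS-QOL symptom severity score, HRQL and EQ-5D, report beside it the FAS 12-month mean change with 95% CI from a repeated-measures mixed model: visits at 3, 6 and 12 months, baseline score as a covariate, unstructured covariance. Label it a sensitivity analysis that assumes data are missing at random. It corrects for leaving that is predictable from recorded scores, not for deterioration that was never recorded.
2. For OTE and satisfaction, add a sensitivity row with all FAS women as denominator. In it, women without a 12-month value who left for documented lack of efficacy or a device- or procedure-related event count as not improved or not satisfied. Say plainly that this extends a rule which 5.6.1 applies only to MBL in the per-protocol population. State also how women missing for other reasons are counted.
3. State how month-12 assessments done at early exit (Protocol 10.6, item C) enter these summaries. Do the same for scores recorded after surgical reintervention. The SAP excludes reintervened women from the MBL analysis but is silent for the secondary endpoints, where good scores after further surgery could be credited to the device.

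Cost: SAP wording and a few extra table rows, with no new data collection. The downside is a model-based figure beside the raw mean, and possibly a slightly less favourable result.
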